12.0 STATISTICAL CONSIDERATIONS

Given it is a sample size of convenience, no sample size calculation was performed.

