				12.0 Error! Bookmark not defined.1
				13.0 Error! Bookmark not defined.15-1
13.1	Error! Bookmaı	k not defined		13.0 End: Bookmark not denned.13-1
_				
13.2	Error! Bookmai			
13.3	Error! Bookmai	k not defined.		
				14.0 1916-1
Append	ices			1

AT2 in Kidney Transplant Page 3 of 22

LIST OF ABBREVIATIONS

ADE Adverse Drug Event
AE Adverse Event
AKI Acute Kidney Injury
ATN Acute Tubular Necrosis

BP Blood Pressure

CrCl Calculated Creatinine Clearance (via Cockcroft Gault equation)

DBP Diastolic Blood Pressure

RAAS Renin-Angiotensin-Aldosterone system

EKG Electrocardiogram

GFR Glomerular Filtration Rate
KDPI Kidney Donor Profile Index
MAP Mean Arterial Blood Pressure
PHI Protected Health Information

SBP Systolic Blood Pressure

HR Heart Rate

SCr Serum Creatinine

UIHHSS University of Illinois Hospital and Health Sciences System
HIPAA Health Insurance Portability and Accountability Act

PHI Protected Health Information

PI Principal Investigator

1.0 PROJECT SUMMARY/ABSTRACT:

The current standard of catecholamine vasopressor management of perioperative hypotension in kidney transplant patients carries significant risks and falls short in many ways. Currently, there is an absence in the scientific literature and research describing the hemodynamic effectiveness and safety of novel pharmacologic agents such as angiotensin II (Giazpreza – Ang II) in perioperative kidney transplant patients. Phase 3 registrational trials have demonstrated the superior safety and efficacy of Ang II (Giapreza) in distributive shock patients compared to traditional vasopressor agents and the novel mechanism of action may provide additional protection in renal transplant patients. The pilot study entails giving informed and consenting kidney transplant recipients Ang II (Giapreza) as their first vasopressor if the need for vasopressors emerge either intraoperatively or postoperatively in kidney transplant recipients. The primary objective is to evaluate the safety and hemodynamic effects of Ang II (Giapreza) in the renal transplant population.

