As described above, the current standard of care of catecholamine vasopressors is associated with significant, detrimental adverse effects associated with the mechanism of vasoconstriction of these agents. The reninangiotensin-aldosterone system (RAAS) is an essential hormonal regulator responsible for maintenance of BP via the actions of angiotensin II (AT2). In 2017, the FDA approved pharmacologic angiotensin II (Giapreza – Ang II) for patients with septic shock or distributive shock from other causes (Giapreza prescribing information). Distributive shock is defined as hypotension refractory to appropriate fluid resuscitation, which occurs frequently during the perioperative renal transplant period. After fluid resuscitation is unsuccessful, the use of catecholamine vasopressor agents are the mainstay of therapy for subsequent blood pressure support. As discussed, the narrow therapeutic window and significant risks associated with current vasopressor agents leave a crucial unmet medical need for safer and more effective therapies. In the ATHOS-3 Phase 3 clinical trial Ang II (Giapreza) was shown to have a more optimal pharmacodynamic profile compared to catecholamine vasopressors. It was found that Ang II (Giapreza) more frequently led to mean arterial pressure (MAP) goal attainment than the standard of care (i.e. norepinephrine) and the median duration of MAP goal attainment was 5 minutes for patients on Ang II (Giapreza); an effect that was sustained throughout the study period. Additionally, the usage of concurrent vasopressors was significantly decreased in subjects using Ang II (Giapreza) compared to the standard of care. Lastly, it was found that Ang II (Giapreza) was a safe medication with the most common ADE (> 4% and > 1.5 x placebo) being: thromboembolic events, thrombocytopenia, tachycardia, fungal infection, delirium, acidosis, hyperglycemia, and peripheral ischemia. Despite the commonality of distributive shock in the intraoperative and postoperative period of renal transplants, there are no data available evaluating Ang II (Giapreza) in this population. The more balanced vasoconstriction of AT2 within the kidney vasculature yields a net result of increased filtration fraction and can preserve kidney function (Fehrer 2012). This has been confirmed with animal and clinical human investigations in patients with the highest known risk of developing acute kidney injury (AKI): septic shock (Lankadeva 2018, Tumlin 2018). Thus, it is hypothesized that the use of Ang II (Giapreza) in the intraoperative and perioperative period for renal transplant patients may lead to improved BP management and more optimal safety outcomes compared to the current standard of care conventional catecholamine vasopressors. Therefore, the purpose of this study is to evaluate the safety and efficacy of Ang II (Giapreza) in improving hypoperfusion among renal transplant patients during the critical peri-op period.

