3.0 OBJECTIVES/AIMS

Study Objectives

Primary: To evaluate the hemodynamic effectiveness of Ang II (Giapreza) for intraoperative and postoperative hypotension in kidney transplant patients. This will be evaluated by the time to reaching BP goal.

Secondary: To evaluate the safety of Ang II (Giapreza) for intraoperative and postoperative hypotension in kidney transplant patients. This will be evaluated by collecting the incidence of common adverse events (ADE) seen from other Ang II (Giapreza) studies in this patient population.

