5.0 ENROLLMENT

The patients at the top of the adult kidney transplant list awaiting DDKT maintained by UIHHSS Transplant will be used to screen for eligibility. See addendum for Eligibility Checklist. Study personnel will perform the screening. A password protected Microsoft Excel sheet will be provided by the Transplant team at UIHHSS. This sheet will have the MRN for the top patients on the kidney transplant list. If patients are initially eligible via inclusion and exclusion review, they will remain on the password protected Microsoft Excel sheet. If they are not eligible, they will be removed after screening by one of the study personnel. This password protected Microsoft Excel sheet will be maintained on the "H" drive behind the University firewall maintained by the CCTS. It is estimated that 40 subjects will be consented/enrolled in order for 20 patients to receive study drug. Twenty patients are the goal for this study and no more than 20 patients will receive study drug.

All eligible study subjects will receive a Research Letter (see addendum for Research Letter) via the mail. One week after the Research Letter is mailed, the subjects that have not called the primary investigator regarding the study will be called via telephone by study personnel to follow-up and provide any additional information regarding the study. This call is to provide information regarding the study, study enrollment criteria, and answer any questions regarding the study. This call is informational only.

If a kidney transplant is offered to the previously contacted subjects the study personnel will be contacted by the Transplant Coordinator when the kidney transplant is confirmed. Once that subject arrives at UI Health for their transplant, subjects will be approached by study investigators in-person, reminded of the study criteria, have ample time to review study information again and the informed consent document, and will be asked to provide signed consent after the appropriate informed consent process is completed. Researchers participating in the consent process will review the informed consent document (ICD) with the recruited subject in its entirety ensuring the subject understands the research purpose, all risks/benefits and the study components of this research.

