7.0 EXPECTED RISKS/BENEFITS

The main anticipated benefit is the potential to establish improved hypotension management of future kidney transplant recipients at UIHHSS. This study could also potentially lead to further outcome studies on the effect vasopressors have on post-operative kidney transplant patients or studies directly comparing individual agents. Conversely, the expected risks are low given the existing data in critically ill patients with septic or other distributive shock. In the ATHOS-3 trial patients, the majority of patients evaluated were septic shock patients with a far greater severity of illness than kidney transplant recipients. In that investigation, there were no lifethreatening ADE's and minimal that were greater than placebo: most common ADE (> 4% and > 1.5 x placebo) being: thromboembolic events, thrombocytopenia, tachycardia, fungal infection, delirium, acidosis, hyperglycemia, and peripheral ischemia. With all medications, there are risks of adverse reactions. All adverse reactions that occur at an incidence of greater than 4% (and > 1.5 x placebo) in the prescribing information will be discussed individually with the subject prior to informed consent. These data points will be collected as noted above in the data collection section. There is also the risk of poorer outcomes and overall health with this agent. As with all investigations, there is a risk of breach of PHI. However, this risk is very low due to the numerous safeguards in place as described above and from using data collection in Redcap. Additionally, password protection and the hospital firewall security further reduce the likelihood of breach of information.

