9.0 DATA ANALYSIS

Statistical Analysis:

Continuous data -> Student t-test

Ordinal data -> Wilcoxon-Mann Whitney test

Nominal data -> Chi-square or Fisher's exact test

Multivariate regression analysis for factors associated with duration of vasopressors and worse kidney outcome

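### Section 9.0 plans no estimate or interval for adverse-event incidences in a single treated cohort of at most 20, so low counts would not show which rates they leave open

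*Combined protocol and SAP*

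**What the plan says.** Safety is a stated aim, although its rank varies. Section 1.0 says: "The primary objective is to evaluate the safety and hemodynamic effects of Ang II (Giapreza) in the renal transplant population". Section 3.0 lists safety as the secondary objective and gives its measure: "This will be evaluated by collecting the incidence of common adverse events (ADE) seen from other Ang II (Giapreza) studies in this patient population". Sections 6.0 and 11.0 list the endpoints, nearly all of them incidences (arrhythmia, ischemia, thrombosis, thrombocytopenia, fungal infection, delirium, insulin infusion).

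The number treated is capped in section 5.0: "Twenty patients are the goal for this study and no more than 20 patients will receive study drug". Section 6.0 describes one cohort of consecutive patients who all receive the drug. It refers once to two arms, when describing data extraction, but no second arm is defined.

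The statistical text is short. Section 9.0 assigns tests by type of data. The line that would cover adverse events is "Nominal data -> Chi-square or Fisher's exact test". Section 12.0 consists of one sentence: "Given it is a sample size of convenience, no sample size calculation was performed". No confidence interval or precision statement for an incidence appears anywhere.

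A 4% figure appears in section 2 (Need for the Study) and section 7.0. It is the threshold for listing reactions seen in earlier data. Section 7.0 refers to "All adverse reactions that occur at an incidence of greater than 4% (and > 1.5 x placebo) in the prescribing information" as the reactions to be discussed before consent.

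**The concern.** The quantity that answers the safety objective is a proportion in a single group. A chi-square or Fisher's exact test, as section 9.0 uses it, compares proportions between groups. It could be applied to subgroups within the cohort, but that would yield a p-value for a difference and not an incidence. A one-sample chi-square test would need a reference rate, and none is named. Followed as written, the plan therefore leaves the safety result as counts.

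At this sample size a count is easily over-read. The reader of a report showing 0/20 or 1/20 for an event is given nothing to indicate that rates well above those of the earlier data remain compatible with the result. Several endpoints will also have denominators below 20, and bare counts hide that.

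**Working it through.** **Inputs**
- Treated patients: at most 20 (sections 5.0 and 13.1).
- Basis for 20: convenience, with no alpha, power, effect or precision target (section 12.0). There is thus no calculation to reproduce. The one related figure that can be checked is the 40 consented subjects in section 13.1: 20 / 0.50 vasopressor use = 40, which agrees.
- Event rates: the documents give no expected rate for this population. I use 4%, 5% and 10% as illustrations. The 4% is the listing threshold in sections 2 and 7.0.

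**Step 1. Exact (Clopper-Pearson) 95% intervals for x events in n patients**

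Lower limit = 2.5% quantile of Beta(x, n − x + 1). Upper limit = 97.5% quantile of Beta(x + 1, n − x). For x = 0 the lower limit is 0 and the upper limit is 1 − 0.025^(1/n).

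| Observed | Exact 95% interval |
|---|---|
| 0/20 | 0 to 16.8% (1 − 0.025^(1/20) = 0.168) |
| 1/20 | 0.1 to 24.9% |
| 2/20 | 1.2 to 31.7% |
| 4/20 | 5.7 to 43.7% |

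**Step 2. Probability of seeing no case in 20 patients: (1 − p)^20**
- p = 4%: 0.96^20 = 0.442
- p = 5%: 0.95^20 = 0.358
- p = 10%: 0.90^20 = 0.122

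Conversely, an event has a 95% chance of appearing at least once only if its true rate is about 13.9% or more (1 − 0.05^(1/20) = 0.139).

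**Step 3. Denominators below 20**

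Sections 6.0 and 11.0 count intraoperative arrhythmia only in patients given the drug during surgery, and postoperative arrhythmia only while the drug is given after surgery. Section 11.0 also removes the data of anyone who withdraws. The documents give no split and no withdrawal rate, so these are illustrations:
- n = 18: no case of a 4% event with probability 0.96^18 = 0.480.
- n = 10: 0/10 has an upper limit of 1 − 0.025^(1/10) = 30.8%, and no case of a 4% event is seen with probability 0.96^10 = 0.665.

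Twenty is therefore the best case for precision.

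**The case against.** The strongest reply is that this is a pilot. A convenience sample without a power calculation is a normal choice, section 7.0 looks ahead to further studies, and no passage says that few or no events will establish safety. Any reader can compute an interval from n/N. All of that stands. The point is not that 20 is too few or that a power calculation is missing. It is that the only method named for this kind of data cannot produce the quantity the objective asks for.

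A second reply is that safety has other cover. Section 11.0 adds relatedness, CTCAE grading, review by the monitoring board after 5, 10, 15 and 20 subjects, and numerical halting criteria. This also stands, and it limits the point: counts can raise an alarm. For example, the Grade 3 criterion of 20% is met at 4/20. But these rules act on events that occur and say nothing about what a low count leaves open.

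A reader might go further and infer that the trial has a 44% chance of missing an event at a rate the protocol itself expects, so that its counts can support no safety conclusion. The documents do not support that. The 4% is a listing floor from earlier data. The listed reactions lie above it, so 44% is the limiting case for them in that source, and section 7.0 says the earlier patients were much more severely ill. The 44% also comes from n = 20 and would be the same with intervals in place. Nor is a blanket refusal to cite absent events justified: 0/20 does exclude, at the 95% level, rates above 16.8%.

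**Conclusion.** The point holds as a gap in analysis and reporting. Safety rests on incidences in one cohort of at most 20, and section 9.0 offers only a between-group test for them. No estimate, interval or precision is planned. At best, zero events leaves rates up to 16.8% open, about four times the 4% listing threshold (16.8 / 4 = 4.2), and one event leaves rates up to 24.9% open. Endpoints with fewer patients at risk are less precise.

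What is limited is reassurance from low or zero counts. The ability of the counts to raise a signal is unaffected. The documents do not show that the investigators intend to call the drug safe on a zero count; that over-reading is a foreseeable risk, not a stated plan.

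The figures assume independent patients with a common event probability, and that removing withdrawn patients' data is unrelated to adverse events. The interval limits do not depend on the 4%. The probabilities of seeing no case do depend on the illustrative rates. Data collection, sample size and stopping decisions are unchanged, but the correction should be made before the counts are known.

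**What to change.** In section 9.0, replace the test for adverse-event incidences with n/N and an exact (Clopper-Pearson) 95% interval for each event. Each event should use its own denominator; for intraoperative arrhythmia, for example, only the patients given study drug during surgery.

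In section 12.0, keep 20 as a convenience sample and add its best-case precision: 0/20 leaves an upper 95% limit of 16.8%, and no case would be seen with probability 44%, 36% or 12% if the true rate were 4%, 5% or 10%. Label these rates as illustrative, and say that 4% is a listing threshold and not a rate expected in this population. Add that smaller denominators give wider limits (0/10, as an illustration: 30.8%).

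State also that zero or low counts will be reported with their upper limit and will not be presented as showing safety beyond that limit.

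The cost is a few sentences, a routine calculation and slightly longer safety tables. No patients are added and clinical management is not touched. The price is a less favourable safety statement.

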13.0 REGULATORY REQUIREMENTS

13.1 INFORMED CONSENT

The patients at the top of the adult kidney transplant list awaiting DDKT maintained by UIHHSS Transplant will be used to screen for eligibility. See addendum for Eligibility Checklist. Study personnel will perform the screening. A password protected Microsoft Excel sheet will be provided by the Transplant team at UIHHSS. This sheet will have the MRN for the top patients on the kidney transplant list. If patients are initially eligible via inclusion and exclusion review, they will remain on the password protected Microsoft Excel sheet. If they are not eligible, they will be removed after screening by one of the study personnel. This password protected Microsoft Excel sheet will be maintained on the "H" drive behind the University firewall maintained by the CCTS. It is estimated that patients

will be required to be screened assuming a consent rate of ~50% and vasopressor utilization rate of ~50% of patients that receive a deceased donor kidney transplant. It is estimated that 40 subjects will be consented/enrolled in order for 20 patients to receive study drug. Twenty patients are the goal for this study and no more than 20 patients will receive study drug.

All eligible study subjects will receive a Research Letter (see addendum for Research Letter via the mail. One week after the Research Letter is mailed, the subjects will be called via telephone by study personnel to follow-up and provide any additional information regarding the study. This call is to provide information regarding the study, study enrollment criteria, and answer any questions regarding the study. This call is informational only.

If a kidney transplant is offered to the previously contacted subjects the study personnel will be contacted by the Transplant Coordinator when the kidney transplant is confirmed. Once that subject arrives at UI Health for their transplant, subjects will be approached by study investigators in-person, reminded of the study criteria, have ample time to review study information again, and will be asked to provide signed consent. Researchers participating in the consent process will review the informed consent document (ICD) with the recruited subject in its entirety ensuring the subject understands the research purpose, all risks/benefits and the study components of this research. If a subject does NOT provide informed consent they will be considered a screening failure and NO data will be extracted and they will not be associated with an alpha-numeric code linked to their MRN.

Given the urgency surrounding the time course immediately before transplant (as noted in the Background/Rationale section above), it was deemed by the research team that the process of sending a Research Letter and following up via telephone is necessary in order to eliminate delay in the pre-op operations, avoid a coercive environment due to the time dependency of pre-op operations, and allow for ample time for information to be exchanged about the study. Additionally, given the lack of routine office visits prior to transplant there is no opportunity to consent these patients in clinic.

Given the time-dependent nature of enrollment in the immediate pre-operative setting and the complexity of enrolling patients with interpreting services, in an effort to avoid coercion or misunderstanding, non-English speaking subjects will not be pursued for enrollment.

13.2 SUBJECT CONFIDENTIALITY

The investigators will review a list of the top patients awaiting kidney transplant maintained by the Transplant Coordinators. This list will be password protected. This list will be kept on the primary investigator's computer stored on the H drive behind the University firewall on the primary investigator's password protected computer in a locked office. It will be available only to the co-investigators. If a patient is screened as eligible and is consented they will be associated with an alpha-numeric code that is linked to their medical record number (MRN). This Study Subject list will be kept as a password protected Excel file on the primary investigator's computer stored on the H drive behind the University firewall on the primary investigator's password protected computer in a locked office. It will be available only to the co-investigators. If a patient requires AT II as their vasopressor and is included in the study, their data will be collected prospectively. These data points will be de-identified, containing no PHI and will be stored in Redcap. All study personnel will have access to the Redcap database. It would be impossible to screen for enrollment without using PHI. This PHI (e.g. MRN) will only be on the list provided by the Transplant Coordinators and the alpha-numeric list of patients included. These lists, as mentioned above, will be kept on a password protected computer.

13.3 UNANTICIPATED PROBLEMS

Though many circumstances have been foreseen, if any unforeseen circumstances arise such as any data breaches or other concerns, these will be reported immediately to the IRB by the primary investigator. Subjects will also be informed pending the instruction of the IRB based off of the problem that has occurred.

AT2 in Kidney Transplant Page 19 of 22

AT2 in Kidney Transplant Page 21 of 22 Version 2.1 6-1-20

APPENDICES

- Appendix 1: Eligibility Checklist (attached)
- Appendix 2: Telephone Script (attached)
- Appendix 3: Angiotensin II (Giapreza) Package Insert (attached)
- Appendix 4: Research Letter

AT2 in Kidney Transplant
Page 22 of 22

Version 2.1
6-1-20
